## 14. STATISTICS

### 14.1 General Considerations

The statistical analysis described in this section will be performed as further outlined in a separate Statistical Analysis Plan (SAP). The SAP will supersede the protocol in the event of any difference between the 2 documents in data analysis and the protocol will be amended of appropriate. Statistical analyses in this study will be descriptive in nature. No statistical inference is planned. Subject disposition, demographics, and baseline characteristics will be summarized. Summary statistics for continuous variables will include the number of subjects, mean, median, standard deviation or standard error, first and third quartiles, minimum, and maximum. Summary statistics for PK parameters will also include geometric mean and coefficient of Variation (CV) (%). For categorical variables, the frequency and percentage will be given.

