**Investigational Medicinal Product(s) (IMPs), Dose, and Mode of Administration:**

Bempedoic acid 180 mg or bempedoic acid 180 mg/ezetimibe 10 mg FCDP will be administered orally once daily for 6 days.

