### 14.2 Determination of Sample Size

A minimum sample size of 16 (8 subjects who receive bempedoic acid [Cohort 1] and 8 subjects who receive bempedoic acid/ezetimibe FCDP [Cohort 2]) evaluable subjects (who complete the 6-day treatment period and the 24-hour breast milk collection in the CRU) is planned for this study. Subjects who are randomized but do not complete the 24-hour breast milk collection in the CRU will be replaced with a new subject on the same treatment to ensure 8 evaluable subjects in each cohort for the final analyses.

The sample size was not based on empirical or hypothesis testing criteria. The sample size was based on clinical and regulatory considerations and precedence in previous ETC-1002 studies (████████). The sample size is considered sufficient to address the primary objectives of the study.

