17.3. PK Analysis for Primary Endpoints

The 1st primary endpoint - **daily infant dosage** (mg/day) of BA or EZE will be calculated as the amount of drug in breast milk collected over 24 hours (starting on Day 6 post study treatment) for individual subjects, where the amount of drug in breast milk is calculated as the sum of total drug concentration in each milk collection multiplied by the expressed milk volume in each milk collection.

Daily infant dosage (Dose_{ij}) = $\Sigma (C_{ij} \times V_{ij})$, where

Dose_{ij} = daily infant dose based on collected drug concentration in breast milk and expressed breast milk volume

C_{ij} = drug concentration in breast milk from each collection

V_{ij} = breast milk volume collected at each nominal timepoint

i = nominal timepoints within 24 hours post study treatment on Day 6

j = subjects (8 in each cohort, 16 in total)

- The 2nd primary endpoint - **relative infant dose (RID)** of BA (for Cohort 1 and 2 respectively) or EZE (for Cohort 2 only) equals the percent of the weight-adjusted maternal dosage consumed by infant via breast milk over 24 hours.

RID (%) = Estimated daily infant dosage (mg/day/kg) / Maternal dosage (mg/day/kg) x 100.

The estimated daily infant dosage will be calculated as the average drug concentration in breast milk over 24 hours after the Day 6 dose administration (C_{avg}) multiplied by 150 mL/day/kg, the estimated standard infant milk intake over 24 hours. Maternal dosage will be calculated as the mean maternal dosage (mg/day per kg baseline body weight determined on Day 1).

Estimated daily infant dosage (mg/day/kg) = C_{avg} (mg/ml) x 150 (ml/day/kg)

Maternal dosage (mg/day/kg) = daily dose of study treatment (mg/day) / baseline body weight (kg)

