Summary statistics of n, arithmetic mean, standard deviation (SD), CV%, minimum, median, maximum, geometric mean (converting back to the original units), and geometric coefficient of variation (GCV%) will be presented for PK concentration data and PK parameters (AUC_{24h} , C_{avg} , C_{max} , T_{max} , C_{trough}) by cohort in summary tables.

- Geometric mean = $\exp [\text{mean of log}(x)]$, exponential of mean of log-transformed concentration data.
- Geometric standard deviation (GSD) = $\exp [\text{SD of log}(x)]$, exponential of standard deviation of log-transformed concentration data.
- GCV% = $\sqrt{\exp (GSD^2) - 1} \times 100$.

The following assessments will also be summarized by cohort:

- Daily infant dosage ($Dose_{ij}$)
- Estimated daily infant dosage
- RID
- M/P ratio

Plots of the following milk concentration-time profiles will be created:

- (A) ETC-1002, (B) ESP15228, (C) ETC-1002-glucuronide on linear scale by cohort.
- (A) EZE, (B) EZE-glucuronide on linear scale for Cohort 2.
- Composite of individual subject (A) ETC-1002, (B) ESP15228, (C) ETC-1002-glucuronide, (D) EZE, (E) EZE-glucuronide on linear scale by cohort.

Box plot of the following parameters from breast milk PK will be created by cohort:

- C_{max} , C_{trough} , C_{avg} , and AUC_{24h} (A) ETC-1002, (B) ESP15228, (C) ETC-1002-glucuronide, (D) EZE, (E) EZE-glucuronide by cohort

All milk and plasma PK concentration data and parameters will be displayed in subject listings.

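### No confidence interval is planned for daily infant dosage or RID, so the precision of the primary estimates from 8 women per cohort goes unreported

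*Protocol*

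**What the plan says.** Protocol 5.1.1 and SAP 2.1 frame the primary objective as estimation: daily infant dosage and RID of bempedoic acid after bempedoic acid alone, and of bempedoic acid and ezetimibe after the fixed combination.

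Protocol 14.1 sets the analysis policy. The analyses are to be descriptive, and it adds: "No statistical inference is planned". It lists n, mean, median, SD or standard error, quartiles and range, and adds a geometric mean and CV% for PK parameters. SAP 8.3 drops the standard error and keeps the SD. The SAP takes precedence on analysis where the two documents differ (Protocol 14.1, SAP 1).

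SAP 17.3 defines RID "of BA (for Cohort 1 and 2 respectively) or EZE (for Cohort 2 only"). SAP 17.4 attaches geometric mean and GCV% to concentrations and to a named set of parameters (AUC, Cavg, Cmax, Tmax, Ctrough). Daily infant dosage and RID come under a separate sentence, "The following assessments will also be summarized by cohort", which names no statistics. Neither document plans a confidence interval for any analysis.

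On sample size, Protocol 14.2 says: "The sample size was not based on empirical or hypothesis testing criteria". It still calls 16 women sufficient for the primary objectives. On dosing, the Protocol synopsis says: "Bempedoic acid 180 mg or bempedoic acid 180 mg/ezetimibe 10 mg FCDP will be administered orally once daily for 6 days".

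**The concern.** A trial whose primary question is how large an exposure is should say how well it has answered that question. Here the sample is 8 women per cohort, no precision target was set, and no interval will be printed. A reader of the RID table will see a central value and the spread between women, but not how far the central value could move in another 8 women. Protocol 4.4 says the results are meant to inform women and their health care providers about treatment during breastfeeding, so over-reading a single figure is the practical risk.

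An interval would also be the only direct evidence for the statement that the sample size is sufficient.

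A second, weaker point follows from the design. Both cohorts take 180 mg of bempedoic acid daily, are randomized 1:1 and have the same milk sampling schedule, yet no combined bempedoic acid summary is specified, even as a supportive result. The SAP does plan overall or total summaries elsewhere, for example for disposition, postpartum history and the adverse event overview.

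**Working it through.** **The plan's own figure.** The stated minimum of 16 evaluable women is 8 + 8. It cannot be reproduced further, because the documents give no confidence level, SD or precision target.

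**Inputs.** Evaluable n is 8 per cohort (Protocol 14.2: "will be replaced with a new subject on the same treatment to ensure 8 evaluable subjects in each cohort"). The two-sided 95% level is my assumption. The between-woman CV is also assumed, at 30%, 50% and 80%: the documents give none, and Protocol 4 says nothing is known about bempedoic acid excretion in milk.

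**Interval for one cohort.** On the log scale, half-width = t(0.975, df) × SDlog / √n, with SDlog = √ln(1 + CV²).

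- n = 8, df = 7: 2.365 / √8 = 0.836 SDlog.
- n = 16 with cohort as a factor, df = 14: 2.145 / √16 = 0.536 SDlog.
- Ratio 0.536 / 0.836 = 0.641, so the combined interval is about 36% narrower on the log scale at any common SDlog.

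As multiples of the geometric mean, exp(± half-width):

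| Assumed CV | SDlog | One cohort, n = 8 | Combined, n = 16 |
|---|---|---|---|
| 30% | 0.294 | 0.78-1.28 | 0.85-1.17 |
| 50% | 0.472 | 0.67-1.48 | 0.78-1.29 |
| 80% | 0.703 | 0.56-1.80 | 0.69-1.46 |

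The combined column applies to bempedoic acid only. Ezetimibe stays at n = 8.

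**What combining assumes.** With equal cohort sizes, the combined geometric mean lies at √r times the Cohort 1 value, where r is the true Cohort 2 to Cohort 1 ratio. For r = 1.25 it lies 12% above Cohort 1 (√1.25 = 1.118); for r = 1.5, 22% above (√1.5 = 1.225). The trial can check this only loosely. The half-width for the ratio is 2.145 × SDlog × √(1/8 + 1/8) = 1.072 SDlog. At CV 50% that is 1.072 × 0.472 = 0.506, an interval of about 0.60 to 1.66 times the observed ratio.

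**Can a reader recover the interval?** For the arithmetic mean, yes, from n and SD. For the geometric mean, only from the individual listings. The printed GCV% would not serve with the usual conversion, because the SAP 17.4 formula uses the geometric SD where the SD of the logs belongs. At a true CV of 50%, GSD = exp(0.472) = 1.604, and √(exp(1.604²) − 1) = 3.48, which prints as 348%.

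**The case against.** A descriptive plan, openly declared, is not an error. Spread is planned throughout, the maximum is shown, all individual values are listed (SAP 17.4) and ad-hoc analyses are allowed (SAP 5.2). For a breastfeeding decision, the range across women may matter at least as much as the precision of a mean. All of this stands, and it makes the point one of reporting.

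A reader might go further and infer that the plan throws away precision, or that it should pool the two cohorts. The documents do not support either step. Because n, SD and listings are kept, an interval can still be derived. By-cohort reporting is what Protocol 5.1.1 and 14.3.2.1 ask for: one answer for each of two products. Nothing in either document shows that ezetimibe or the combination tablet leaves bempedoic acid in milk unchanged, so a combined figure cannot be called the better-supported estimate. A cohort factor removes the difference from the residual variance, but it does not make the average describe either product.

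It can also be said that a confidence interval is inference, which Protocol 14.1 rules out. An interval used for estimation tests no hypothesis and suits this objective, but the sentence as written would need adjusting.

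**Conclusion.** The point holds as a minor improvement. Neither document plans an interval for the two primary endpoints, the SAP omits the standard error that the protocol allows, and it does not clearly commit to a geometric mean for daily infant dosage or RID. With 8 women per cohort the unreported uncertainty is material: roughly −22% to +28% at an assumed CV of 30%, and −44% to +80% at 80%.

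These figures rest on log-normal values, the assumed CVs and exactly 8 contributing women. The last may not hold. SAP 6.2 admits women with one evaluable milk concentration, whereas Protocol 14.3.2 requires the complete 24-hour collection. SAP 17.4 makes Cavg, and hence RID, not evaluable with fewer than 3 points above the quantification limit.

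The 36% gain from a combined bempedoic acid estimate also needs equal log variance, and its meaning needs similar milk exposure from the two products. It is therefore optional and secondary to the by-cohort intervals.

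**What to change.** In SAP 17.3 and 17.4, state that daily infant dosage and RID will be reported by cohort and analyte as a geometric mean with a two-sided 95% CI from log-transformed values, with the number of women contributing to each. Label the interval as descriptive estimation with no hypothesis test. Reword the no-inference sentence in Protocol 14.1 to match; that section already foresees amending the protocol where the documents differ.

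Optionally, add a supportive combined bempedoic acid estimate from log values with cohort as a factor. Show it beside the Cohort 2 to Cohort 1 ratio and its CI, with a note that it is interpretable only if the two products give similar bempedoic acid milk exposure. By-cohort results stay primary.

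The GCV% formula in SAP 17.4 can be corrected in the same revision.

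The cost is wording in the SAP and one protocol sentence, plus a few table rows. No new data, samples or subjects are needed. The remaining downside is that the narrower combined interval could be over-read, which is why the ratio must stand next to it.

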### 14.2 Determination of Sample Size

A minimum sample size of 16 (8 subjects who receive bempedoic acid [Cohort 1] and 8 subjects who receive bempedoic acid/ezetimibe FCDP [Cohort 2]) evaluable subjects (who complete the 6-day treatment period and the 24-hour breast milk collection in the CRU) is planned for this study. Subjects who are randomized but do not complete the 24-hour breast milk collection in the CRU will be replaced with a new subject on the same treatment to ensure 8 evaluable subjects in each cohort for the final analyses.

The sample size was not based on empirical or hypothesis testing criteria. The sample size was based on clinical and regulatory considerations and precedence in previous ETC-1002 studies (████████). The sample size is considered sufficient to address the primary objectives of the study.

### 14.3 Analysis Population

#### 14.3.1 Safety Population

The Safety Population (SP), used for all the safety summaries, is defined as all subjects who received at least 1 dose of IMP.

#### 14.3.2 Pharmacokinetic Population

The PK Population will include all subjects who complete the 24-hour breast milk collection after IMP administration on Day 6.

#### 14.3.2.1 Primary Analyses

- Daily infant dosage and RID of bempedoic acid will be summarized for Cohort 1 subjects who receive once daily bempedoic acid for 6 consecutive days.
- Daily infant dosage and RID of bempedoic acid and ezetimibe will be summarized for Cohort 2 subjects who received once daily bempedoic acid/ezetimibe FCDP for 6 consecutive days.
- RID will be calculated as the ratio of total infant dose per kg body weight and maternal dose per kg body weight, multiplied by 100.

#### **14.3.2.2 Secondary Analyses**

The PK parameters of bempedoic acid, ezetimibe, and metabolites (ESP15228, bempedoic acid glucuronide, and ezetimibe-glucuronide) in mature breast milk will be calculated using standard noncompartmental methods, including:

- breast milk AUC over the 24-hour collection interval;
- average milk concentration based on milk AUC;
- peak and trough milk concentrations as well as time to reach peak milk concentrations; and
- plasma concentrations at 24 hours after the last dose on Day 6.

Pharmacokinetic calculations will be performed, if appropriate, using commercial software such as Phoenix™ WinNonlin® Version 6.4 or higher (Certara USA Inc.).

Descriptive statistics will be provided for the PK parameters.

Other parameters may be added as appropriate; the final PK parameters reported will be detailed in the SAP.

#### **14.4 Safety Analyses**

General safety data in this study includes AEs, clinical laboratory parameters, PEs, vital signs, and body weight.

Treatment-emergent AEs (TEAEs) are defined as AEs that begin or worsen after randomization and the first dose of IMP through Day 13. TEAEs will be summarized by System Organ Class (SOC), Preferred Term, and severity. Serious TEAEs, IMP-related TEAEs, TEAEs leading to withdrawal of IMP, and deaths will be also summarized.

Clinical laboratory parameters including hematology and blood chemistry, PE findings, vital signs, and body weight will be summarized and listed using descriptive statistics.

## **15. DIRECT ACCESS TO SOURCE DATA/DOCUMENTS**

### **15.1 Study Monitoring**

The Sponsor (or its authorized representative) has the obligation to follow this study closely to ensure that the study is conducted in accordance with the protocol, International Conference on Harmonisation (ICH) and GCP guidelines, national and international regulatory requirements, and the current Declaration of Helsinki throughout its duration by means of personal visits to the Investigator's facilities and other communications.

These visits will be conducted to evaluate the progress of the study, verify the rights and well-being of the subjects are protected, and verify the reported clinical study data are accurate, complete, and verifiable from source documents. This includes review of ICFs, results of tests performed as a requirement for participation in this study, and any other medical records (e.g., laboratory reports, clinic notes, IMP dispensing log, pharmacy records, subject-completed diaries, or telephone logs) required to confirm information contained in the eCRFs.

The monitoring strategy for the study foresees a risk-based monitoring approach, in line with the relevant FDA recommendations and will be described in detail by the study specific risk-based monitoring plan.

A monitoring visit should include a review of the essential clinical study documents (regulatory documents, case report forms, medical records and source documents, drug disposition records, and subject ICFs, etc.) as well as discussion on the conduct of the study with the Investigator and staff.

The monitor should conduct these visits as frequently as appropriate for the clinical study. The Investigator and staff should be available during these visits for discussion of the conduct of the study as well as to facilitate the review of the clinical study records and resolve/document any discrepancies found during the visit.

All monitoring activities will be reported and archived. In addition, monitoring visits will be documented at the clinical site by signature and date on the study-specific monitoring log.

### **15.2 Audits and Inspections**

Representatives of the Sponsor or its authorized clinical quality assurance group may visit a clinical site at any time during the study to conduct an audit of the study in compliance with regulatory guidelines and company policy. These audits will require access to all study records, including source documents, for inspection and comparison with the eCRFs. Subject privacy must be respected. The Investigator and clinical site personnel are responsible for being present and available for consultation during routinely scheduled site audit visits conducted by the Sponsor or its authorized representative.

The clinical study may also be inspected by the FDA or other regulatory authority to verify that the study was conducted in accordance with protocol requirements, as well as the applicable regulations and guidelines.

In the event the Investigator is contacted by regulatory authorities who wish to conduct an inspection of the clinical site, the Investigator will promptly notify the Sponsor of all such requests and will promptly forward a copy of all such inspection reports.

## **16. QUALITY CONTROL AND QUALITY ASSURANCE**

To ensure compliance with GCP and all applicable regulatory requirements, the Sponsor (or designee) may conduct a quality assurance audit.

## 17. ETHICS

### 17.1 Institutional Review Board Approval

Before initiation of the study, the Investigator must obtain approval or favorable opinion of the research protocol, ICF, and any material related to subject recruitment from an IRB. The IRB must comply with the provisions specified in 21 Code of Federal Regulations (CFR) Part 56, ICH and GCP guidelines, and applicable pertinent state and federal requirements.

IRBs must be constituted according to the applicable laws. It is the responsibility of the clinical site to submit the protocol, IB, subject informed consent, subject recruitment materials (if applicable), and other documentation as required by the IRB for review and approval. A copy of the written approval must be provided to the Sponsor.

The documentation should clearly mention the approval/favorable opinion of the protocol, the subject ICF, and subject recruitment materials (if applicable), including respective version dates. The written approval and a list of the voting members, their titles or occupations, and their institutional affiliations must be obtained from the IRBs and provided to the Sponsor prior to the release of clinical study supplies to the clinical site and commencement of the study. If any member of the IRB has direct participation in this study, written notification regarding his or her abstinence from voting must also be obtained.

Clinical sites must adhere to all requirements stipulated by their respective IRB. This includes notification to the IRB regarding: protocol amendments, updates to the ICF, recruitment materials intended for viewing by subjects, aggregate safety reports required by regulatory competent authorities, serious and unexpected AEs, reports and updates regarding the ongoing review of the study at intervals specified by the respective IRB, and submission of final study reports and summaries to the IRB.

It is the responsibility of each clinical site to submit information to the appropriate IRB for annual review and annual re-approval.

The Investigator must promptly inform their IRB of all SAEs or other safety information reported from the subject or the Sponsor.

### 17.2 Ethical Conduct of the Study

The Investigator agrees, when signing the protocol, to conduct the study in accordance with ethical principles that have their origin in the current revision of the Declaration of Helsinki and are consistent with ICH/GCP, applicable regulatory requirements, and policies and procedures as outlined by the ethical requirements for IRB review and ICFs.

The Investigator agrees to allow monitoring and auditing of all essential clinical study documents by the Sponsor or its authorized representatives and inspection by the FDA or other appropriate regulatory authorities. Monitoring and auditing visits by the Sponsor or authorized designee will be scheduled with the appropriate staff at mutually agreeable times periodically throughout the study.

The Investigator will assure proper implementation and conduct of the study, including those study-related duties delegated to other appropriately qualified individuals. The Investigator will assure that study staff cooperates with monitoring and audits and will demonstrate due diligence

in recruiting and screening study subjects. The Investigator must sign and return to the Sponsor the “Investigator’s Signature” page (see [Appendix 4](#)) and provide a copy of their current curriculum vitae. For this study and all studies conducted under an investigational new drug application (IND), the Investigator must sign and return a completed Form FDA 1572 “Statement of Investigator” to the Sponsor (or designee).

### **17.3 Written Informed Consent**

The Principal Investigator will ensure that the subject is given full and adequate oral and written information about the nature, purpose, and possible risks and benefits of the study. Subjects must also clearly understand that they are free to discontinue from the study at any time. The subject should be given the opportunity to ask questions and allowed time to consider the information provided.

The subject’s signed and dated informed consent must be obtained before conducting any study procedures on the Sponsor agreed ICF. Updates to the ICF during the conduct of the study will be communicated by written letter from the Sponsor to the Investigator. The ICF should be provided in the appropriate language of the subject population.

The Principal Investigator(s) must maintain the original, signed ICF. A copy of the signed ICF must be given to the subject.

